3.1 Primary Endpoint

3.1.1 Overall response rate (ORR) with the combination of blinatumomab and pembrolizumab in adult subjects with relapsed or refractory B-cell acute lymphoblastic leukemia be defined as the CR rate plus the CRh rate after 1 or 2 cycles of combination therapy. CR is defined as <5% lymphoblast in the bone marrow without evidence of circulating lymphoblasts or extramedullary disease. CRh is defined as for CR except with platelet count >50,000/microliter, hemoglobin >7 g/dL, and ANC >500/microliter. ORR will be compared to historical controls treated with blinatumomab alone.

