5.1.6 Response assessment

Response will be assessed by bone marrow aspiration and biopsy on:

- Cycle 1, Day 12, 13, or 14
- Cycle 1, Day 29 + 8 days
- Cycle 2, Day 29 + 8 days
- Cycle 3, Day 29 + 8 days
- Cycle 4, Day 29 + 8 days
- Cycle 5, Day 38 + 8 days

Bone marrow aspiration and biopsy should occur at the time of any relapse or suspected relapse.

Bone marrow aspirates and biopsies should be sent for standard morphology, flow cytometry, karyotype, and *in situ* hybridization for any abnormalities documented on screening bone marrow studies.

Minimal residual disease testing on a first pull bone marrow aspirate should be sent overnight to University of Washington for analysis.

Requisition form is available in **Appendix C**.

For patients with extramedullary disease at diagnosis, repeat imaging using the same modality as at diagnosis is to be performed to assess response on:

- Cycle 1, Day 12, 13, or 14
- Cycle 1, Day 29 + 8 days
- Cycle 2, Day 29 + 8 days

Cycle 5, Day 38 + 8 days

Repeat imaging should occur at the time of any relapse or suspected relapse.

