Labs: CBC with differential, CMP (sodium, potassium, chloride, bicarbonate, BUN, creatinine, glucose, calcium, total bilirubin, AST, ALT, alkaline phosphatase), direct bilirubin, amylase and lipase

Adverse Event Assessment

Concomitant Medications

Cycle 2

Day 1

Administration of Blinatumomab 28 mcg/d CIV days 1-28

Physical exam, performance status, vital signs, weight

Labs: CBC with differential, CMP (sodium, potassium, chloride, bicarbonate, BUN, creatinine, glucose, calcium, total bilirubin, AST, ALT, alkaline phosphatase), direct bilirubin, amylase and lipase

Adverse Event Assessment

Concomitant Medications

Day 15

Administration of Pembrolizumab 200 mg IV once

Labs: CBC with differential, CMP (sodium, potassium, chloride, bicarbonate, BUN, creatinine, glucose, calcium, total bilirubin, AST, ALT, alkaline phosphatase), direct bilirubin, amylase and lipase

Adverse Event Assessment

Concomitant Medications

Day 29 + 8 Days

Labs: CBC with differential

Procedures: Bone marrow aspiration and biopsy. Send for standard histology, flow cytometry, cytogenetics (karyotype and *in situ* hybridization for previously documented abnormalities required, additional testing allowed per institutional standard of care) and quantitative PCR for BCR-ABL1 p190 and/or p210 if previously positive.

Correlative research samples to be collected with bone marrow aspirate and peripheral blood for flow cytometry and bone marrow aspirate for western blot (See **Section 6.5**)

MRD assessment: 6-color flow cytometry on bone marrow aspirate on at least 0.5×10^6 mononuclear cells when technically possible. MRD assessment to be done on first pull bone marrow aspirate, redirected bone marrow aspirate should be performed as needed for first pull bone marrow aspirate. MRD samples to be sent to University of Washington for analysis (**Section 7.1.3, Appendix C**).

Lumbar puncture with **Methotrexate administration** and CSF studies: Cell count with differential, cytology and flow cytometry.

Imaging: Diagnostic CT chest, abdomen, and pelvis with IV and oral contrast in patients with palpable lymphadenopathy or masses at diagnosis. Patients unable to get contrasted study should get non-contrasted CT scans.

Day 36

Administration of Pembrolizumab 200 mg IV once

Labs: CBC with differential, CMP (sodium, potassium, chloride, bicarbonate, BUN, creatinine, glucose, calcium, total bilirubin, AST, ALT, alkaline phosphatase), direct bilirubin, amylase and lipase

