7.1.3 Methods for Evaluation of Measurable Disease

Bone marrow:

Bone marrow aspiration of 2-3 ml should be prepared for standard morphologic evaluation by aspirate smears on glass slides. Additional aspirate (5-10 mL) should be obtained for flow cytometry, cytogenetics (karyotype and *in situ* hybridization), and molecular analyses.

Bone Marrow Aspirate or Biopsy samples to be collected at study specified time points and sent to the University of Washington for MRD analysis (see **Appendix C**). MRD assessment to be done on first pull bone marrow aspirate. If necessary, aspirate needle should be re-directed to obtain first pull aspirate for MRD studies.

This analysis is to be performed on all patients, and billed to their insurance.

Requisition form for samples available in **Appendix C**.

If bone marrow aspirate cannot be obtained (dry tap) or no spicules present in aspirate, 2 bone marrow core biopsies should be obtained for flow cytometry and cytogenetics. Institutional practice supersedes.

Bone marrow core needle biopsy should be 1-2 cm in length for adequate evaluation.

Blood:

Evaluation of peripheral blood should occur by morphologic evaluation of a peripheral blood smear. This should be performed at the time of each bone marrow biopsy and when clinically indicated.

Extramedullary Disease

Lymph node enlargement, tumors:

For patients with a known mediastinal mass or lymphadenopathy or palpable masses on physical exam, FDG-PET/CT scan will be performed with diagnostic CT scans of the chest, abdomen, and pelvis with IV contrast except when contraindicated or felt unsafe by the investigator. When PET-CT not feasible, CT chest/abdomen/pelvis with contrast alone should be performed.

For patients with pathologic lymph node enlargement or tumors, all measurements should be taken and recorded in metric notation using a ruler or calipers. All baseline evaluations should be performed as closely as possible to the beginning of treatment and never more than 14 days before the beginning of the treatment.

The same method of assessment and the same technique should be used to characterize each identified and reported lesion at baseline and during follow-up. Imaging-based evaluation is preferred to evaluation by clinical examination when both methods have been used to assess the antitumor effect of a treatment.

CNS disease:

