7.1.4.1 Bone Marrow and Blood

Complete Response (CR):

- No circulating blasts or extramedullary disease
- Bone marrow with normal trilineage hematopoiesis and <5% blasts
- Absolute neutrophil count (ANC) >1,000/microliter
- Platelet count >100,000/microliter
- No disease recurrence for 28 days

Complete Response with Partial Hematologic Recovery (CRh):

- As for CR but platelet count >50,000/microliter, hemoglobin >7 g/dL, and ANC >500/microliter

Overall Response Rate (ORR):

- Defined as the sum of the CR rate and CRh rate.

Refractory disease:

- Failure to achieve CR at end of induction

Progressive Disease (PD):

- Increase of at least 25% in the absolute number of circulating or bone marrow leukemic blasts or appearance of new extramedullary disease

Relapsed Disease:

- Re-appearance of blasts in the bone marrow (>5%) or blood or in any extramedullary site after achieving a CR or CRh

Flow MRD Negativity:

- Absence of detectable leukemic blasts above the 0.01% (1×10^{-4}) level by minimum 6-color flow cytometry

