7.1.4.3 Mediastinal Disease

Complete Response:

- Complete resolution of mediastinal enlargement by CT or if FDG-avid/PET positive prior to therapy, mass of any size permitted if PET negative

Complete Response Unconfirmed (CRu):

- Residual mediastinal enlargement that has regressed by >75% in the sum of the product of the greatest perpendicular diameters (SPD)

Partial Response (PR):

- >50% decrease in the SPD of the mediastinal enlargement

Progressive Disease (PD):

- >25% increase in the SPD of the mediastinal enlargement

No response (NR):

- Failure to qualify for CR, CRu, PR, or PD

Relapse:

- Recurrence of mediastinal enlargement after achieving CR or CRu

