7.1.4.4 Nodal Disease

Complete Response:

- Complete resolution of lymph node enlargement by CT or, if FDG-avid or PET positive prior to therapy, lymph node enlargement of any size permitted if PET negative

Partial Response (PR):

- ≥50% decrease in the SPD of up to 6 largest dominant masses with no increase in size of other nodes

Progressive Disease (PD) or Relapse:

- any new enlarged lymph node mass >1.5 cm in any axis, ≥50% increase in the SPD of more than one node, or ≥50% increase in the longest diameter of a previously identified node >1 cm in short axis
- lesions PET positive if FDG-avid or PET positive prior to therapy

No response (NR):

- Failure to qualify for CR, PR, or PD

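### At the two visits that decide CR/CRh, the schedule and Section 6.2 give CT only, while 5.1.6 and 7.1.3 require the baseline modality, so scoring of a residual mass that was PET positive at baseline depends on which section a site follows

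*Combined protocol and SAP*

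**What the plan says.** **Endpoint.** Section 3.1 has the response rate "defined as the CR rate plus the CRh rate after 1 or 2 cycles of combination therapy". It adds that "CR is defined as <5% lymphoblast in the bone marrow without evidence of circulating lymphoblasts or extramedullary disease", and CRh differs from CR only in the blood counts. Section 7.1.4.1 repeats the condition: "No circulating blasts or extramedullary disease".

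**Baseline imaging.** For patients with palpable nodes or masses, 6.1.18 prefers PET-CT with diagnostic CT and accepts CT alone where PET is not possible. Section 7.1.3 says the same.

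**Response imaging, the rule.** For patients with extramedullary disease, 5.1.6 states that "repeat imaging using the same modality as at diagnosis is to be performed to assess response on" four listed occasions: Day 12 to 14 and Day 29 + 8 of Cycle 1, Day 29 + 8 of Cycle 2, and Day 38 + 8 of Cycle 5. Section 7.1.3 adds: "The same method of assessment and the same technique should be used to characterize each identified and reported lesion at baseline and during follow-up".

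**Response imaging, the visit instructions.** At Cycle 1 and Cycle 2 Day 29 + 8, Section 6.2 reads "Imaging: Diagnostic CT chest, abdomen, and pelvis with IV and oral contrast in patients with palpable lymphadenopathy or masses at diagnosis", with no mention of PET. The schedule table has a CT row for these visits. Its PET/CT row covers screening, end of treatment and relapse, and footnote f ties PET/CT to screening, end of treatment and follow-up.

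**Extramedullary CR.** Sections 7.1.4.3 to 7.1.4.5 give two routes: complete resolution on CT or, for disease that was PET positive before therapy, a negative PET whatever the residual size. The mediastinal wording is "mass of any size permitted if PET negative".

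**The concern.** CR and CRh both require the absence of extramedullary disease, and one of the two ways to show that is a negative PET. The visit instructions do not provide a PET at either visit that determines the endpoint, although the response-assessment section does for anyone imaged by PET-CT at baseline.

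Two sites could therefore classify the same patient differently: cleared marrow, and a shrunken mass that was PET positive at screening. The classification feeds the 18-patient and 24-patient decisions in 10.5.1. It also determines whether the patient continues, because 5.1.3 takes patients without CR/CRh after two cycles off study, and they would not reach the PET that the schedule table places at end of treatment.

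**Working it through.** **1. The passages side by side** (taking the modality at diagnosis to be that of the screening scan)

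| Time point | 5.1.6 | Schedule table | 6.2, 6.2.1 or 6.4 |
|---|---|---|---|
| Cycle 1 Day 12-14 | baseline modality | none | none |
| Cycle 1 Day 29 + 8 | baseline modality | CT | CT |
| Cycle 2 Day 29 + 8 | baseline modality | CT | CT |
| Cycle 5 Day 38 + 8 | baseline modality | PET/CT | CT |
| Relapse | repeat imaging | PET/CT | CT |

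Rows two and three bear on the primary endpoint.

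**2. Who is affected.** The conflict matters only if all three conditions hold: extramedullary disease at baseline, imaged by PET and PET positive, and still visible on CT at the response visit. A CT-only baseline makes CT the same modality. Complete resolution on CT meets CR without PET.

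**3. Where such a lesion falls on CT alone.** For nodal (7.1.4.4) and other extramedullary disease (7.1.4.5), a lesion that has not resolved on CT and has no PET result cannot be shown to meet CR. It falls to PR if it meets the 50% reduction rule, or to NR if it meets none of the categories. Neither counts in the response rate. Mediastinal disease (7.1.4.3) also has CRu, for regression of more than 75%, but nothing says whether CRu satisfies the condition for CR or CRh.

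**4. The plan's design figures.** Inputs from 10.5.1: p0 = 0.29, p1 = 0.54; 18 patients first, stop at 7 or fewer responses; 24 in total, reject at 11 or more.

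- P(stop) = sum over x = 0 to 7 of C(18,x) p^x (1-p)^(18-x)
- P(reject) = sum over x = 8 to 18 of C(18,x) p^x (1-p)^(18-x) × P(Y ≥ 11 - x), with Y binomial(6, p)

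At p = 0.29: P(stop) = 0.880 and P(reject) = 0.0499. At p = 0.54: P(reject) = 0.801. The stated 0.88, 0.05 and 0.80 all reproduce.

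**5. Illustrative effect.** Let e be the share of patients with PET-positive extramedullary disease, and m the share of their true responses that leave a PET-negative mass on CT. Neither is in the documents; both are assumed. Suppose every such response is scored as a failure and response rates do not differ by extramedullary status. The scored rate is then p × (1 - e × m), and the expected number of responders lost among 24 is 24 × 0.54 × e × m.

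| e | m | Scored rate at 0.54 | Power | Type I error | Responders lost of 24 |
|---|---|---|---|---|---|
| 0 | - | 0.540 | 0.801 | 0.050 | 0 |
| 5% | 25% | 0.54 × 0.9875 = 0.533 | 0.783 | 0.046 | 0.16 |
| 10% | 50% | 0.54 × 0.95 = 0.513 | 0.722 | 0.035 | 0.65 |
| 20% | 50% | 0.54 × 0.90 = 0.486 | 0.630 | 0.024 | 1.30 |

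The type I error column puts 0.29 × (1 - e × m) into the same formula.

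**The case against.** The strongest reply is that the plan already contains the right rule. Section 5.1.6 is the response-assessment section, it names both visits, and a site that follows it does PET. This is then an inconsistency between sections rather than a defective design. That is a fair description, but it does not remove the problem: sites work from the visit list and the schedule table, and both say CT.

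It can also be said that the size is unknown and the direction conservative. Both are true. The lower power figures need the upper end of both assumed ranges, every site following 6.2, and every such mass counted as failure. There is no added risk of a false claim of efficacy.

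Four stronger readings are tempting, and the documents do not support them.

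- A reader might infer that the plan expressly scores a residual mass without PET as non-response. No section says so. For nodal and other extramedullary lesions it follows from the categories; for mediastinal masses CRu leaves it open.
- A reader might infer that the response criteria always need PET. They do not: CT resolution is a full alternative, and a CT-only baseline is allowed.
- A reader might infer false relapses at end of treatment, because 7.1.4.4 lists "lesions PET positive if FDG-avid or PET positive prior to therapy" under progression or relapse. If 6.2 was followed and masses persisting on CT were not counted as CR, patients still on treatment had resolved on CT. A later PET-positive lesion in them is not shown to be false. The sections also disagree on whether PET is done at that visit.
- A reader might infer that the 14-day imaging limit in 7.1.3 conflicts with the 21-day screening window in 6.1. Section 6.1 allows for exceptions stated elsewhere, and 7.1.3 states one.

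**Conclusion.** The contradiction stands. Sections 5.1.6 and 7.1.3 require the baseline modality, while the schedule table, footnote f and 6.2 leave PET out at the two visits that decide CR/CRh. For a patient with PET-positive extramedullary disease at baseline and a residual mass on CT, following 6.2 removes one of the two routes to CR. The response call can then differ between sites.

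The number of such patients is not in the documents. On the assumed ranges (5-20% of patients, 25-50% of their responses), the expected loss is 0.16 to 1.30 responders of 24. Power falls from 0.80 to between 0.78 and 0.63, and type I error falls from 0.050 to between 0.046 and 0.024. These figures illustrate the direction and possible scale; they are not estimates. The textual conflict is certain, and its effect on the trial's result is not.

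Two lesser conflicts belong to the same repair: the Cycle 1 Day 12-14 scan appears only in 5.1.6, and the table gives PET/CT at end of treatment and relapse where 6.2.1 and 6.4 give CT.

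**What to change.** 1. Reconcile the schedule table, footnote f, 6.2, 6.2.1 and 6.4 with 5.1.6, so that patients with PET-positive disease at screening have PET/CT in place of CT at Cycle 1 and Cycle 2 Day 29 + 8. At minimum, require PET/CT for a residual mass that was PET positive at baseline before it is classed as non-response at Cycle 2.
2. State in 7.1.4 how a residual CT mass with no PET result counts toward CR/CRh, and whether mediastinal CRu does.
3. Reconcile the Day 12-14 scan: list it in the table and 6.2, or remove it from 5.1.6.
4. Give one modality each for end of treatment and relapse in all sections.

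The cost is amendment wording and somewhat higher imaging expense in the subset with PET-positive extramedullary disease. The PET/CT replaces a CT already scheduled. Sample size and decision rules do not change.

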6.2.1 End of Treatment Visit (Day 38 + 8 days of Cycle 5)

On Day 38 + 8 days of Cycle 5:

Physical exam, performance status, vital signs, weight

Labs: CBC with differential, CMP (sodium, potassium, chloride, bicarbonate, BUN, creatinine, glucose, calcium, total bilirubin, AST, ALT, alkaline phosphatase), direct bilirubin, amylase and lipase

Procedures: Bone marrow aspiration and biopsy. Send for standard histology, flow cytometry, cytogenetics (karyotype and in situ hybridization for previously documented abnormalities only) and quantitative PCR for BCR-ABL1 p190 and/or p210 if previously positive.

MRD assessment: 6-color flow cytometry on bone marrow aspirate on at least 0.5×10^6 mononuclear cells when technically possible. MRD assessment to be done on first pull bone marrow aspirate, redirected bone marrow aspirate should be performed as needed for first pull bone marrow aspirate. MRD samples to be sent to University of Washington for analysis (**Section 7.1.3, Appendix C**).

Imaging: Diagnostic CT chest, abdomen, and pelvis with IV and oral contrast in patients with palpable lymphadenopathy or masses at diagnosis. Patients unable to get contrasted study should get non-contrasted CT scans.

Lumbar puncture with **Methotrexate administration** and CSF studies: Cell count with differential, cytology, and flow cytometry.

Adverse Event Assessment

Concomitant Medications

6.3 Follow-up Procedures

Patients will be followed for a minimum of 2 years from study entry or until death, whichever occurs first. Patients removed from study for unacceptable adverse events will be followed until resolution or stabilization of the adverse event. Patients taken off study to undergo allogeneic or autologous stem cell transplantation will be censored for relapse and survival as of the date they begin non-protocol therapy. Patients refusing protocol-defined follow-up or lost to follow-up will be censored as to their status on the day of last contact.

Patients will be seen every 3 months for 2 years after completion of therapy. At these visits the following assessment will be performed:

Physical exam, vital signs, weight

Labs: CBC with differential

Concomitant Medications

6.4 Relapse

At suspected or documented relapse the following assessments should be performed:

Physical exam with vital signs, and weight.

Labs: CBC with differential, CMP (sodium, potassium, chloride, bicarbonate, BUN, creatinine, glucose, calcium, total bilirubin, AST, ALT, alkaline phosphatase), direct bilirubin

Bone marrow aspiration and biopsy. Send for standard histology, flow cytometry, cytogenetics (karyotype and *in situ* hybridization) and quantitative PCR for BCR-ABL1 p190 and p210 if previously positive.

Molecular testing (FoundationOne™ Heme testing)
See **Section 6.5.1.1** for details of collection.

Lumbar puncture with CSF studies: Cell count with differential, cytology and flow cytometry.

Imaging: Diagnostic CT chest, abdomen, and pelvis with IV and oral contrast in patients with history of palpable lymphadenopathy or masses at diagnosis or palpable lymphadenopathy or masses at relapse. Patients unable to get contrasted study should get non-contrasted CT scans.

Concomitant Medications

6.5 Correlative Studies

The goal of the planned laboratory correlative studies is to determine PD-L1 and PD-L2 protein expression on lymphoblasts and in the bone marrow microenvironment at diagnosis, to determine changes in PD-L1 and PD-L2 expression with blinatumomab exposure, and correlate changes in PD-L1 and PD-L2 expression with disease response. We also aim to determine how changes in cytokine expression with therapy correlate with PD-L1 and PD-L2 expression changes.

6.5.1 Sample Collection Guidelines

All samples collected must be labeled with study ID, Patient ID number, date of collection, time point of collection and time of collection.

6.5.1.1 Molecular testing (FoundationOne™ Heme testing)

Bone marrow samples will be sent for FoundationOne™ Heme mutational analysis at diagnosis and at time of relapse.

If a patient's health insurance will not cover the cost of FoundationOne Heme Testing then a sample should not be sent. This will not be considered a protocol deviation.

Research requisition form for samples available in **Appendix B**.

Samples collection guidelines:

Bone marrow aspirate (preferred):

Collect 0.5 to 2 mL bone marrow aspirate in an EDTA tube.

Peripheral blood:

If unable to obtain bone marrow aspirate and patient has peripheral blood blast count >20%, then send peripheral blood for mutational analysis as follows:

Collect 10 mL whole blood in EDTA, sodium citrate, or sodium heparin tube.

Bone marrow core biopsies:

If unable to provide adequate bone marrow aspirate or peripheral blood sample, then provide formalin-fixed paraffin embedded bone marrow core biopsy sample.

Formalin-fixed paraffin-embedded (FFPE) block OR 14 unstained slides + 1 haematoxylin + eosin stained slide.

Note: EDTA recommended for decalcification for the minimum amount of time. Hydrochloric acid and formic acid should not be used for dec

Shipping instructions:

Place the FoundationOne Heme Requisition Form (**Appendix B**) and samples into the FoundationOne Heme Specimen Kit.

Place the FoundationOne Heme Specimen Kit (including the FoundationOne Heme Requisition Form) into the provided shipping pack and seal the shipping pack.

3. Complete the pre-printed shipping labels (if necessary) and apply to shipping pack.

4. Ship completed specimen kit (requisition form, samples) to:

Accessioning, Clinical Laboratory Foundation Medicine, Inc.

[name]

[contact] [contact]

Place all materials into the FedEx pack provided with the Specimen Kit and drop pack at your site's designated FedEx pick up location or call FedEx to schedule a pick up.

